3.6.1 Physician's Leasion Assessment (PLA) Analyses

PLA related parameters will be summarized at lesion level and at subject level.

At each visit or applicable visit, the following analyses will be performed:

• Descriptive statistics will be provided for the per-subject mean change from baseline in PLA for each post-baseline scheduled visit separately for the PP population.

- Descriptive statistics will be provided for the per-subject mean change from baseline in PLA for each post-baseline scheduled visit separately for the ITT population.
- The number and percent of subjects having all lesions with PLA score of 0 will be provided for each post-baseline scheduled visit separately (PP population).
- The number and percent of subjects having all lesions with PLA score <= 1 will be provided for each post-baseline scheduled visit separately (PP population).

The following treatment group comparisons will be performed for PLA endpoints from Cohort 2:

- Tretment group comparisons will be made for the change from baseline in per-subject mean PLA score at each post-baseline scheduled visit for the PP population. These comparisons will be made using a repeated measures mixed model where treatment group and time (visit) are included as class variables and baseline per-stubject mean PLA score and number of treated lesions will be included as continuous covariates. The per-subject PLA measures over time will be treated as repeated measures by including subject as a random effect. An unstructured variance covariance matrix will be assumed. If the model experiences convergence issues with the unstructured variance covariance assumption, then a compound symmetric assumption will be used. The difference in least square means for the treatment groups along with corresponding 95% confidence intervals and p-values will be provided for each of the scheduled visits. A plot of the treatment group least square means (and 95% confidence intervals) across time (visit) will be provided.
- Tretment group comparisons will be made for the change from baseline in per-subject mean PLA score at each post-baseline scheduled visit for the ITT population using LOCF for missing data. The model for analysis and output will match that of the PP population analysis and output described above.
- A logistic regression will be used to make treatment comparions in the proportion of subjects having all lesions with PLA score of 0 (PP population). This analysis will be performed at each scheduled visit separately. This model will include a class variable for treatment group as well as baseline per-subject mean PLA score and number of treated lesions as a continuous covariate. Model based odds ratios, corresponding 95% confidence intervals and p-values will be provided at each scheduled visit.
- Similarly, a logistic regression will be used to make treatment comparions in the proportion of subjects having all lesions with PLA score of <= 1. This model and output will be the same as described for the PLA score = 0 analysis.

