Informed Consent	X							
Inclusion Criteria/Exclusion Criteria	X	X ¹						
Subject Identifier	X ²							
Medical history/demographics	X							
Fitzpatrick Skin Type Assessment	X ³							
Vital Signs	X	X ⁴						X
Prior Medications/Therapies	X ⁵							
Clinical Chemistry and CBC ⁶	X							X
Urine Pregnancy Test ⁷	X	X						X
Target Lesion Identification ⁸	X							
Physician's DPN Lesion Assessment ⁹	X	X	X	X	X	X	X	X
Subject Self-Assessment Scale ¹⁰	X	X	X	X	X	X	X	X
Lesion Dimensions ¹¹	X	X	X	X	X	X	X	X
Standardized Photography ¹²	X	X	X	X	X	X	X	X
Subject Randomization		X ¹³						
Local Skin Reactions		X ¹⁴	X ¹⁴	X	X ¹⁴	X	X	X
Study Medication Application		X ¹⁵	X ¹⁵		X ¹⁵			
Wound Care ¹⁶		X	X		X			
Subject Instructions	X	X	X	X	X	X	X	X
Concomitant therapies ¹⁷		X	X	X	X	X	X	X
Adverse Events ¹⁸		X	X	X	X	X		

¹Subject inclusion/exclusion criteria will be re-assessed prior to study enrollment during Visit 2.

²Investigational sites will assign a unique five-digit subject identifier to each subject at Visit 1. This subject identifier will be used in all study documentation for the duration of the study.

³Each subject's skin must be assessed during Visit 1 using the Fitzpatrick Skin Type Assessment. Refer to Section 9.5.1 for the scale.

⁴Vital signs [including temperature, pulse, respiratory rate, blood pressure, and weight (Visit 1 only)] will be measured by a qualified staff member at Visit 1, Visit 2 prior to study enrollment, and at Visit 8.

⁵Prior medications/therapies will be collected for a time-period of 13 days prior to Visit 2. Refer to Section 7.7 for a list of permitted and restricted concomitant medications.

⁶A complete blood count (including hematocrit, hemoglobin, platelet count, red blood cell count, white blood cell count and differential (absolute and %) including basophils, eosinophils, lymphocytes, monocytes and neutrophils and a clinical chemistry panel including albumin, alkaline phosphatase, alanine aminotransferase (ALT), aspartate aminotransferase (AST), blood urea nitrogen (BUN), bicarbonate, calcium, chloride, creatinine, glucose, lactate dehydrogenase (LDH), phosphorus, potassium, sodium, total bilirubin, total protein, and uric acid.

⁷Woman of child bearing potential will be required to have a urine pregnancy test at Visit 1, at Visit 2 prior to enrollment and at Visit 8.

⁸The treating investigator will identify up to 4 Target DPN Lesions.

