12.2. Statistical Analysis of Efficacy Data

Efficacy summaries and analyses (where appropriate) will be based on the per protocol (PP) population of all treated subjects completing all treatment visits and Visit 8 with no major protocol violations. In addition, efficacy summaries may be presented for the intent to treat (ITT) population of all treated subjects with at least one post-baseline visit, using last observation carried forward (LOCF) to impute missing data. Efficacy endpoints will include summary statistics (frequency distributions, proportions, means, medians and standard deviations, as appropriate) by visit for the following parameters: Physician's DPN Lesion Assessment scale results per treated lesion, subject responders defined by Physician's DPN Lesion Assessment scale outcome, and changes from baseline treated lesion diameter.

Comparative inferential analyses will be conducted for data collected from subjects in Cohort 2. The primary efficacy comparisons between the two Cohort 2 treatment groups will be made on the per-subject mean change across all treated lesions in Physician's DPN Lesion Assessment scale from baseline to the final visit using an ANCOVA model. A similar secondary analysis will be performed on the pre-subject mean percent of treated lesions that are clear (PLA=0), and a similar analysis based on clear or near-clear lesions (PLA < 2). Another secondary analysis will be performed on subject responders with all treated lesion PLA scores = 0, as well as a similar analysis on subject responders with all treated lesion PLA scores < 2. An analysis of change from baseline lesion diameter will be conducted using the same methodology as the primary efficacy analysis. All analyses will be conducted at each post-baseline visit where possible. Summaries will also be presented by subject Fitzpatrick Skin Type.

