3.1 GENERAL STATISICAL CONSIDERATIONS

Descriptive statistics (mean, standard deviation [Std Dev], median, minimum [Min], and maximum [Max]) will be used for continuous variables; number and percentage of subjects will be used for discrete variables. In general, the last measurement prior to the first dose of study treatment will be used as the baseline value. Nominal visits will be used for by-visit summaries and analyses.

All treatment group comparisons will be made at the 0.05 level using a two-sided hypothesis test, unless otherwise specified.

Summaries will be presented by each arm, ie, Cohort 1 FST 5, Cohort 1 FST 6, Cohort 2 Arm A, Cohort 2 Arm B, and Total (combining both cohorts subjects).

All tabulations of summary statistics, graphical presentations, and statistical analyses will be performed using SAS[®] Version 9.2 or higher.

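### SAP 3.6.1 no longer singles out the final visit as the primary Cohort 2 comparison, tests the arms at every visit at 0.05 with no order, and omits the treatment-by-visit term that a Visit 8 contrast needs

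*SAP*

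**What the plan says.** Protocol 12.2 defines the primary analysis for the randomised cohort: "The primary efficacy comparisons between the two Cohort 2 treatment groups will be made on the per-subject mean change across all treated lesions" on the PLA scale, "from baseline to the final visit using an ANCOVA model". The same paragraph adds: "All analyses will be conducted at each post-baseline visit where possible". The protocol therefore has a named final-visit primary with by-visit analyses beside it.

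SAP 3.6.1 replaces the ANCOVA with a repeated measures mixed model. Its text is: "Tretment group comparisons will be made for the change from baseline in per-subject mean PLA score at each post-baseline scheduled visit", first for the PP population and then for ITT with LOCF. For the model terms it says "treatment group and time (visit) are included as class variables", with baseline mean PLA and the number of treated lesions as covariates. For the output, "95% confidence intervals and p-values will be provided for each of the scheduled visits". Two responder definitions (all lesions at PLA 0, all lesions at PLA 0 or 1) are also tested at each visit. SAP 3.1 sets the level: "All treatment group comparisons will be made at the 0.05 level using a two-sided hypothesis test, unless otherwise specified".

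SAP 3.6 and section 4 still speak of a primary efficacy analysis and a primary endpoint, but no part of the SAP attaches a visit to either. Section 4 explains the new model and the added covariate. It says nothing about the status of the final visit.

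**The concern.** A primary analysis without a time point is not fully specified. After unblinded data in an open-label study of 24 randomised subjects, the report could present any visit's p-value as the primary efficacy result and still be consistent with SAP 3.6.1.

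The visits do not answer the same question. In Cohort 2 the PLA at Visit 3 (Day 15) and Visit 5 (Day 29) is taken before any retreatment at that visit, and Visit 4 (Day 22) falls between them. All three precede the possible third application on Day 29. Only Visits 6 to 8 (Days 50, 78 and 106) follow the full schedule. The secondary objective, durability of response, also points to the late visits.

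The choice has a practical consequence. Section 4 limits the abbreviated report to the primary and key secondary efficacy analyses. It also drops three ANCOVA tests that were tied to the last evaluation or measurement. No remaining arm comparison is singled out at the end of the study.

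**Working it through.** The documents give no familywise error rate, power or sample-size derivation, so there is no plan figure to reproduce beyond 0.05 per test.

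**Inputs from the documents**
- Cohort 2 has 24 subjects allocated 1:2, so 24 × 1/3 = 8 in Arm A and 24 × 2/3 = 16 in Arm B.
- Each test is two-sided at 0.05 (SAP 3.1).
- The number of post-baseline PLA visits in Cohort 2 is inconsistent. The schedule tables (Protocol Table 3, SAP Table 2) mark PLA at Visits 3 to 8, which is six. The text (Protocol 8.1.2, SAP 2.4.2.1) assigns the Visit 4 PLA to Cohort 1 only, which leaves five: Visits 3, 5, 6, 7 and 8.
- The number of by-visit p-values follows from this. There are four sets (mean PLA in PP, mean PLA in ITT, two responder definitions), so 4 × 6 = 24 or 4 × 5 = 20.

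**Assumption.** The between-visit correlation is not given. It is varied from 0 to 0.9, as compound symmetric (CS) and as AR(1).

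**Step 1: independent visits.** P(at least one p < 0.05) = 1 − (1 − 0.05)^k.
- k = 5: 1 − 0.95^5 = 22.6%
- k = 6: 1 − 0.95^6 = 26.5%

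**Step 2: correlated visits.** Trials with no arm effect were simulated, 40,000 per setting. Each used two-sided pooled t-tests on 8 + 16 − 2 = 22 degrees of freedom at each visit. This approximates the SAP's model without its covariates, for the six or five PP mean-PLA tests only. Chance of at least one p < 0.05:

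| Correlation | 5 visits, CS | 5 visits, AR(1) | 6 visits, CS | 6 visits, AR(1) |
|---|---|---|---|---|
| 0.5 | 18.4% | 20.3% | 21.3% | 24.0% |
| 0.7 | 15.0% | 17.4% | 16.9% | 20.1% |
| 0.8 | 13.2% | 15.5% | 14.4% | 17.4% |
| 0.9 | 10.4% | 12.0% | 11.2% | 13.7% |

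The last visit tested alone rejected in 4.8% to 5.3% of runs, as it should. With correlations from 0 to 0.9, the any-visit rate runs from 10.4% (five visits, CS, 0.9) to 26.5% (six independent visits).

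**Step 3: the model as written.** With treatment effect τ and visit effect v, and no interaction, the arm difference at visit j is (τ_B + v_j) − (τ_A + v_j) = τ_B − τ_A. This is the same at every visit, so the output would repeat one number and one test. That number is a weighted average over visits. Three of the six visits, or two of the five, precede the possible third application. It is not the protocol's final-visit contrast. The promise of a difference at each visit suggests that an interaction was intended, and Steps 1 and 2 presuppose it.

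**The case against.** The case on the other side has five parts.

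- **By-visit testing is not new.** A reader might infer that the SAP turned one comparison into many. Protocol 12.2 already planned every analysis at each post-baseline visit where possible, and the SAP reduces testing overall: three hypothesis tests are dropped and the Subject Self-Assessment becomes descriptive. This stands. What changed is that the final visit lost its named primary status.
- **The primary was not withdrawn.** Section 4 announces a change of model to capture changes over time and keeps the term primary endpoint. One can read the protocol's final visit as still in force. That is possible, but the SAP does not say so, and the governing analysis text treats all visits alike.
- **There is no decision rule to inflate.** SAP section 3 calls the summaries mainly descriptive, Protocol 12.1 says the study is to inform the sizing of later ones, and section 4 says a separate DPN indication is no longer sought. This stands as a limit on the consequences. The inflation arises only if a difference at any visit may be claimed. Yet the SAP does specify p-values at 0.05, and nothing in it rules such a claim out.
- **A single error rate cannot be read off the plan.** A reader might settle on a figure such as 18%. That needs, for example, five visits with CS correlation 0.5 (18.4%). No section gives the correlation, and the visit count is contradictory, so only the range is supportable. A larger figure that adds the responder endpoints would need the covariate-adjusted logistic models of SAP 3.6.1, which were not simulated here.
- **Read literally, the model yields one test at about 5%.** True, but that test is not the protocol's primary either.

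**Conclusion.** The concern holds as a gap in specification. The protocol has a final-visit primary comparison. The SAP has a primary analysis with no primary visit, arm p-values at every visit at two-sided 0.05, no testing order, and no declaration of this in section 4.

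If any visit may be claimed, the false-positive chance on PP mean PLA is about 10% to 27%, two to five times the nominal 5%. This rests on 8 v 16 subjects, five or six visits, an assumed correlation of 0 to 0.9, and an intended treatment-by-visit term. The ITT repeat and the responder tests add further p-values that this range does not count.

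The documents do not support saying that the SAP introduced by-visit testing, or that the plan carries one definite error rate. Because the comparison is a small, largely descriptive phase 2 one, the point should be corrected but does not undermine the study.

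**What to change.** In SAP 3.6.1:

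1. State that the one primary test is Arm B v Arm A in per-subject mean PLA change from baseline at Visit 8, in the PP population, estimated from the mixed model.
2. Add a treatment-by-visit term, so that the model can yield a Visit 8 contrast.
3. Label the ITT repeat, all other visits and the responder endpoints supportive, with estimates and 95% confidence intervals but no significance claim.
4. Reconcile the schedule tables with the assessment text on whether Cohort 2 has a Visit 4 PLA.

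This restores a 5% primary test and keeps every by-visit estimate. If the sponsor preferred to keep all visits co-primary, Bonferroni would require 0.05/6 = 0.0083 per visit for six visits, or 0.05/5 = 0.0100 for five, which is a heavy price with 24 subjects.

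The cost is a few sentences and no new data. The downside is that an isolated early-visit p-value can no longer be claimed.

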Lastly, the ANCOVA model described in the protocol for the primary endpoint has been replaced with a repeated measures mixed model in order to capture changes over time in the primary efficacy endpoint and account for within subject correlation in the repeated measures over time. The number of treated lesions is also being added as a covariate in the primary efficacy model and the logistic regression model for responders which was not considered in the protocol.

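### The Cohort 2 primary PLA model has no treatment-by-visit term, so as written it gives one arm difference for all visits instead of the promised by-visit and final-visit comparisons

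*SAP*

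**What the plan says.** SAP Section 3.6.1 sets out the Cohort 2 comparison of change from baseline in per-subject mean PLA: "These comparisons will be made using a repeated measures mixed model where treatment group and time (visit) are included as class variables". Baseline mean PLA and number of treated lesions enter as continuous covariates. Within-subject correlation is handled "by including subject as a random effect. An unstructured variance covariance matrix will be assumed", with compound symmetry as the fallback. No treatment-by-visit term is listed.

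The same bullet promises the difference in least-square means for the two arms, and says the corresponding "95% confidence intervals and p-values will be provided for each of the scheduled visits". It also asks for a plot of the arm means over visits. The ITT analysis with LOCF uses the same specification: "The model for analysis and output will match that of the PP population analysis and output described above".

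Protocol Section 12.2 defines the primary comparison as the change "from baseline to the final visit using an ANCOVA model". SAP Section 4 replaces that ANCOVA with the mixed model "in order to capture changes over time in the primary efficacy endpoint" and to account for within-subject correlation. It also records one further change: "The number of treated lesions is also being added as a covariate in the primary efficacy model". It mentions no interaction.

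**The concern.** The listed terms and the promised output do not fit together. With treatment and visit as main effects only, the two arms' fitted profiles are parallel by construction. The table of differences, intervals and p-values by visit would repeat one row, and the planned plot would show two parallel lines.

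The figure printed against Visit 8 would not be a Visit 8 comparison. It would be an average over all post-baseline visits, with weights set by the estimated covariance. If the effect of abrasion builds up or fades between Day 15 and Day 106, that average is biased for the protocol's primary comparison. It could hide a late difference or report one that has disappeared. Because the ITT analysis copies the model, it would not reveal the problem.

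**Working it through.** The documents give no SD, effect size or power figure, so there is no planned number to reproduce. The structural point is algebra; only its size needs assumptions.

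**From the documents.** The model terms and covariance are as in SAP 3.6.1. Tests are two-sided at 0.05 (SAP 3.1). Cohort 2 has 24 subjects (SAP 1.1) randomized 1:2 (SAP 2.3.2), so 24/3 = 8 in Arm A and 16 in Arm B. There are six post-baseline PLA visits if Visit 4 (Day 22) counts, as in SAP Table 2, and five if it does not, as in SAP 2.4.2.1. Both were run.

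**Assumed.** SD 0.6; errors compound symmetric (correlation 0.6) or AR(1) (0.8); complete data; 1–4 lesions per subject at baseline grade 2 or 3; baseline slope −0.3; 24 − 4 = 20 degrees of freedom. Arm differences at Days 15, 22, 29, 50, 78 and 106 (the five-visit case drops Day 22):
- growing: 0, −0.1, −0.2, −0.4, −0.5, −0.6
- early only: −0.6, −0.6, −0.5, −0.3, −0.1, 0
- constant: −0.4 throughout
- null: 0 throughout

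**Step 1: the difference at visit j.** Let T be arm, B baseline mean PLA and L number of lesions.
- As listed: E[Y_ij] = μ + τT_i + v_j + β1·B_i + β2·L_i. The least-square-mean difference is τ at every j.
- With treatment-by-visit: the difference is τ + δ_j.

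On one simulated six-visit data set, the listed model with a random intercept gave −0.033 at all six visits. The interaction model on the same data gave 0.277, 0.027, −0.022, 0.096, −0.200 and −0.377. Their plain mean is −0.199/6 = −0.033. The listed model with an unstructured matrix gave 0.14 at all six visits. The covariance choice therefore moves the single pooled number but does not make it visit-specific.

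**Step 2: what τ averages.** T, B and L are constant over visits, so the estimate targets Σ w_j·d_j / Σ w_j, where d_j is the true difference at visit j and the weights w come from the inverse covariance matrix. Compound symmetry gives equal weights. AR(1) 0.8 gives weight 1 to the first and last visits and 1 − 0.8 = 0.2 to those between.

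| Path (true Visit 8 value) | Visits | Compound symmetry | AR(1) |
|---|---|---|---|
| Growing (−0.60) | six | −1.8/6 = −0.30 | (−0.6 − 0.2×1.2)/2.8 = −0.30 |
| Growing (−0.60) | five | −1.7/5 = −0.34 | (−0.6 − 0.2×1.1)/2.6 = −0.315 |
| Early only (0) | six | −2.1/6 = −0.35 | (−0.6 − 0.2×1.5)/2.8 = −0.32 |
| Early only (0) | five | −1.5/5 = −0.30 | (−0.6 − 0.2×0.9)/2.6 = −0.30 |

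**Step 3: simulation at Visit 8.** 4,000 runs per cell; ranges cover both error structures; Monte Carlo SE at most 0.8 percentage points. The known-covariance column isolates bias from the missing term.

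| Path | Visits | Listed model, unstructured | Listed model, covariance known | With treatment-by-visit, unstructured |
|---|---|---|---|---|
| Growing: estimate; coverage | six | −0.30; 60–61% | −0.30; 72–73% | −0.60; 94–95% |
| Growing: estimate; coverage | five | −0.31 to −0.35; 66–68% | −0.31 to −0.34; 75–79% | −0.60; 94–95% |
| Early only: rejection | six | 42–45% | 32–34% | 5–6% |
| Early only: rejection | five | 35–38% | 25–27% | 5–6% |
| Constant: estimate; coverage | both | −0.40; 85.5–88.3% | −0.40; 95% | no bias |
| Null: rejection | six | 14–15% | – | 5–6% |
| Null: rejection | five | 11% | – | 5–6% |

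The gap between the third and fourth columns is small-sample error from estimating an unstructured matrix on 24 subjects. The same error produces the null-row excess, since a compound-symmetry fit of the listed model rejects in 4.6–5.4% there. In the growing path the interaction model rejects at Visit 8 in 56–59% of runs and the listed model in 36–43%.

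**Step 4: other inputs.** With SD 0.7, correlation 0.6 under either structure (treated as known) and a difference of 0, 0, −0.2, −0.4, −0.6, −0.8, the listed model averaged −0.34 or −0.36 at Visit 8 and the interaction model −0.80. With a difference fading from −0.8 to zero at Visit 8, the listed model rejected there in 25% or 39% of 1,000 trials, against 4.5% or 5.6% with the interaction.

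**The case against.** The best defence is that the term is implied. The SAP does not exclude it, and a request for differences by visit makes sense only if it is present. Identical rows would also be noticed in the first draft table. That may well describe the intent, but the text gives a term list that cannot produce its own output, so two competent programmers could report different primary results. Where separate fits per visit were meant, as for the responder models, the SAP says so: "This analysis will be performed at each scheduled visit separately".

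Some of the supporting argument is weaker than the core. A visit main effect does capture change over time common to both arms, so the aim stated in SAP Section 4 is only partly defeated. That section does not list visit as an added term either, so its silence on the interaction proves little. It openly replaces the final-visit ANCOVA, and the SAP names no primary visit, so Visit 8 as the primary contrast comes from Protocol 12.2. That section also asks for analyses at each visit where possible.

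Both arms are treated on the same days, so a changing arm difference is plausible but not documented. The simulation inputs are assumed, and under a constant difference there is no bias.

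The stakes are also limited. By-visit descriptive summaries for each arm and the responder models are unaffected. No power is claimed (Protocol 12.1), summaries are mainly descriptive (SAP 3), and an abbreviated report is planned (SAP 4). On the other hand, SAP Section 4 drops the ANCOVA tests of percent clear, percent clear or near-clear, and diameter. This model is then the only formal arm comparison left on a continuous efficacy endpoint.

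**Conclusion.** The concern holds. As listed, the primary model yields one common arm difference whatever covariance structure is used, and this rests on no assumption. It cannot supply the visit-specific results promised in SAP 3.6.1 or the final-visit comparison in Protocol 12.2.

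The size depends on how the true difference moves over visits, which the documents do not say. Under the assumed paths, the Visit 8 estimate is roughly half the true −0.60, or a zero Visit 8 difference is rejected in about a quarter to a third of runs from bias alone, and more once small-sample error is added. The harm is a misleading primary estimate rather than a failed trial. It should be corrected before the analysis is run.

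A smaller wording point: a random subject effect together with an unstructured matrix describes the same covariance twice. This is redundant but leaves the marginal model unchanged.

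**What to change.** In SAP 3.6.1, add treatment-by-visit as a fixed effect for both the PP and ITT analyses. State that the Visit 8 least-square-mean difference is the primary contrast, carried over from Protocol 12.2, and that other visits are supportive. Specify the within-subject covariance once: an unstructured repeated matrix with the existing compound-symmetry fallback and no additional random subject effect. A small-sample degrees-of-freedom method is optional, since the Visit 8 interaction contrast stayed close to 5% without one.

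The cost is one or two sentences and one model term, with no new data. The Visit 8 interval widens somewhat: its mean SE is about 0.26–0.27 (before covariate adjustment, 0.6 × √(1/8 + 1/16) = 0.26), against 0.22–0.23 for the listed model with compound symmetry. The listed model's unstructured SE of 0.19–0.20 is not a fair comparator, because that estimate's actual spread was 0.25–0.33.

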
Efficacy will be evaluated based on assessment of each treated Target DPN Lesion based on a four-point Physician's DPN Lesion Assessment Scale. Sites will be required to take standardized color photographs of each of the identified Target DPN Lesions to assist with the documentation of the location of each of the DPN Lesions throughout the study.

Number of Patients to be Enrolled:
 
A total of 36 subjects will be enrolled to the study. Twelve evaluable subjects will be enrolled to the first cohort (6 subjects with a Fitzpatrick Skin Type of 5 and 6 subjects with a Fitzpatrick Skin Type of 6) and a total of 24 subjects will be randomized to the study in cohort 2.

Number of Study Sites:
 
This study will be conducted at up to 2 US clinical treatment site.

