2.3.2 Randomization

Cohort 1 of this study is an open label study. Subject randomization is not applicable for this part of the study.

Subjects that are determined to be eligible for treatment in Cohort 2 will be randomized in a 1:2 ratio to one of the following treatment arms.

- ARM A: A-101 40% Solution; No medical abrasion to the Target DPN Lesions Treatment Days 1, 15 and 29
- ARM B: A-101 40% Solution applied after medically abrading the Target DPN Lesions; Treatment Days 1, 15 and 29

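### The Cohort 2 primary mixed model is over-parameterised and ambiguous, falls back directly to equal-variance compound symmetry, and lists no treatment-by-visit term although differences are reported by visit

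*SAP*

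**What the plan says.** Protocol 12.2 planned the primary Cohort 2 comparison on per-subject mean change in PLA "from baseline to the final visit using an ANCOVA model". SAP 4 records that "the ANCOVA model described in the protocol for the primary endpoint has been replaced with a repeated measures mixed model", in order to follow change over time and allow for within-subject correlation.

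SAP 3.6.1 gives the new model:

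- **Fixed effects:** treatment group and visit as class variables, baseline mean PLA and number of treated lesions as continuous covariates. No treatment-by-visit term is listed.
- **Random effect:** "The per-subject PLA measures over time will be treated as repeated measures by including subject as a random effect".
- **Covariance:** "An unstructured variance covariance matrix will be assumed". The text does not say whether this means the residual matrix or the matrix of the random effects.
- **Fallback:** "If the model experiences convergence issues with the unstructured variance covariance assumption, then a compound symmetric assumption will be used". There is no intermediate step.
- **Output:** least-squares mean difference, 95% interval and p-value for each scheduled visit, plus a plot of the arm means over time.

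No method for degrees of freedom or small-sample standard errors is named. SAP 3.1 adds only that "All treatment group comparisons will be made at the 0.05 level using a two-sided hypothesis test" and that SAS 9.2 or higher will be used. On size, the protocol synopsis says "a total of 24 subjects will be randomized to the study in cohort 2", and SAP 2.3.2 says "Subjects that are determined to be eligible for treatment in Cohort 2 will be randomized in a 1:2 ratio".

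**The concern.** A primary model should lead any two programmers to the same fit. This text allows three:

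1. A random subject intercept plus an unstructured residual matrix, which is redundant.
2. An unstructured matrix applied to a single random intercept. That matrix is 1 × 1, so the model is compound symmetry from the start.
3. An unstructured residual matrix by subject with no separate random effect. This is sound, but the SAP does not say it.

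Two consequences could reach the reported intervals. A convergence warning sends the analysis to a structure with one variance for every visit, which gives wrong by-visit intervals if the spread of PLA change differs over time. And a model without treatment-by-visit estimates a single arm difference, so the differences requested at each visit would be identical by construction, with parallel curves in the plot.

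The ITT repeat uses the same model, so it would share these weaknesses.

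**Working it through.** **Inputs.** 24 subjects at 1:2 give 24 × 1/3 = 8 and 24 × 2/3 = 16. Alpha is 0.05 two-sided (SAP 3.1). Post-baseline PLA visits number six by the Cohort 2 schedule (Protocol Table 3, SAP Table 2), but five by Protocol 8.1.2 and SAP 2.4.2.1, which restrict the Visit 4 PLA to Cohort 1. The documents give no SD, correlation or power figure (Protocol 12.1), so there is no figure to reproduce, and every SD below is an assumption.

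**Step 1: redundancy.** An unstructured matrix for T visits has T(T+1)/2 parameters.

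- Six visits: 6 × 7/2 = 21; with a random intercept 22, rank 21.
- Five visits: 5 × 6/2 = 15; with a random intercept 16, rank 15.
- Compound symmetry: 2; with a random intercept 3, rank 2.

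One parameter is surplus in each case, including the fallback. What cannot be identified is the split between the two components. The marginal covariance is still fully determined, so a fit that converges gives the same means and standard errors.

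**Step 2: the fallback with by-visit differences.** Under compound symmetry the working SD at each visit is roughly the root mean square of the visit SDs. For SDs rising evenly from 0.55 to 0.80, the squares sum to 0.3025 + 0.36 + 0.4225 + 0.49 + 0.5625 + 0.64 = 2.7775. The mean is 0.463 and the root 0.680, so at Visit 8 the SE ratio is 0.680/0.80 = 0.85. The normal tail beyond 1.96 × 0.85 = 1.67 is about 9.5% two-sided. For 0.4 to 0.9 the squares sum to 2.71, the root mean square is 0.672, the ratio is 0.672/0.9 = 0.75, and the tail is about 14%.

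Simulation agrees. It used 3,000 runs under no arm effect, 8 v 16 subjects, six visits, complete data, treatment-by-visit fitted, and a correlation of 0.6 (exchangeable) or 0.85 (autoregressive). Each range runs from t on 20 df to a normal reference.

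| Assumed SD, Visit 3 to Visit 8 | SE / true SD at Visit 8 | Type I error at Visit 8 |
|---|---|---|
| constant 0.7 | 0.99 | 4.4% to 5.9% |
| 0.55 to 0.80 | 0.85 | 7.9% to 9.4% |
| 0.4 to 0.9 | 0.77 | 12.4% to 15.0% |
| 0.9 to 0.4 | 1.61 | 0.3% to 0.4% |

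The error at Visit 3 runs the other way: 0.1% to 0.3% for the 0.4 to 0.9 case, and 12.5% to 14.6% for 0.9 to 0.4. A separate check gave 12% at Visit 8 for 0.4 to 0.8, 7.7% for 0.5 to 0.7, 4.3% for equal SDs and 0.3% for 0.8 to 0.4.

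**Step 3: the terms as listed.** Without treatment-by-visit, the unstructured fit had a model SE of about 0.74 of the true SD in all scenarios. Type I error was 13.4% to 14.9% with t on 20 df and 15.7% to 17.0% with a normal reference. The single difference is a weighted average over visits. Its weights come from 21 covariance parameters estimated on 24 subjects, and the model-based SE ignores that uncertainty. Kenward-Roger (first 800 runs) reduced the error only to 7.1% to 8.6%. Compound symmetry with the listed terms was near nominal (4.5% to 5.3% with t on 20 df), but it too reports one average difference rather than a Visit 8 difference.

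**Step 4: the repaired model.** With an unstructured residual matrix and treatment-by-visit, Visit 8 error was 4.4% to 5.8% with t on 20 df and 6.1% to 7.0% with a normal reference. With Kenward-Roger it was 3.7% to 5.4%, on about 21 df. Simulation error at a true 5% is √(0.05 × 0.95/800) = 0.8 points for the Kenward-Roger runs and √(0.05 × 0.95/3000) = 0.4 points elsewhere.

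**The case against.** The best defence is that the passage is loosely worded rather than wrong. Treating the measures as repeated, with an unstructured matrix, can describe the ordinary residual-covariance model, and SAP 4's stated aim of allowing for within-subject correlation fits that reading. With by-visit differences, that model is close to nominal. This stands as a possible reading, but the SAP names a random effect and lists no interaction, so the reader has to supply both corrections.

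A reader might infer that the redundancy itself makes the intervals wrong. It does not (Step 1). Nor has it been shown that the redundant fit fails: it was not run here, so the route to the fallback is a risk rather than a demonstrated event.

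A reader might also infer that the Visit 8 interval must come out too narrow. The documents give no SD. Lesions start at PLA 2 or 3 on a scale with floor 0, so spread could grow as subjects separate into cleared and not cleared, or shrink if most lesions clear.

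The unstated df method is missing detail on its own. A software default could be adequate, and a normal reference with 18 to 22 df would give only 6.3% to 6.6%.

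Replacing the final-visit ANCOVA is disclosed and explained in SAP 4. Restoring it as a second reference result would create two candidate primary answers, so that is not proposed.

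**Conclusion.** The specification is over-parameterised and ambiguous, and two of its features can produce misleading by-visit intervals. The compound-symmetry fallback misstates them whenever the variance differs by visit, in a direction not known in advance. The missing treatment-by-visit term conflicts with the requested output and, with an unstructured matrix, inflates type I error even if the variance is constant. These are alternative routes to error and their sizes do not add: the fallback figures assume by-visit differences are fitted, and the 13% to 15% assumes they are not.

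The redundancy and the missing term follow from the text alone. The error rates rest on assumed SDs and correlations, normal errors, complete data and a full 8 v 16.

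Severity is moderate. SAP 3 calls the summaries mainly descriptive, Protocol 12.1 looks to later studies, and SAP 4 says a separate DPN indication is no longer sought. The arms are also compared by responder logistic regressions, so this is the primary but not the only inferential comparison.

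**What to change.** In SAP 3.6.1:

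1. Delete the random subject effect and state that the unstructured matrix is the within-subject residual covariance across visits.
2. Add treatment-by-visit, so that the reported differences are specific to each visit.
3. Name Kenward-Roger standard errors and degrees of freedom. This does not replace item 2.
4. Replace the compound-symmetry fallback with an ordered list of structures whose variance is free by visit: heterogeneous Toeplitz, then heterogeneous AR(1) or heterogeneous compound symmetry.
5. Reconcile the Visit 4 PLA for Cohort 2 between the schedule tables and Protocol 8.1.2 / SAP 2.4.2.1, since it sets whether the matrix is 5 × 5 or 6 × 6.

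Apply the same text to the ITT repeat. The cost is SAP wording, a few code options and slightly wider intervals (about 6% to 7% wider than with normal quantiles at 22 to 18 df). No data collection changes, apart from whatever item 5 settles.
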